5.3 Efficacy Endpoints and Analyses

All the efficacy endpoints and analyses will be done by using FAS (Full analysis set), and Treatment Completer Analysis Set.

5.3.1 Co-Primary Endpoint Analysis

The co-primary efficacy endpoints consist of three comparisons of the percent change from baseline to Week 12 in LDL-C: FDC vs. placebo, FDC vs. EZE; and FDC vs. BA.

In cases where triglycerides (TG) is >400 mg/dL or LDL-C is ≤ 50 mg/dL, a measured LDL (LDL-M) will be used instead of LDL-C for the analysis of that time point. If both values are available, the LDL-M will be used.

An ANCOVA with treatment group and randomization stratification as factors and baseline LDL-C as a covariate will be performed to compare treatment groups (LDL-C: FDC vs. placebo, FDC vs. EZE; and FDC vs. BA) for the primary endpoint using the FAS. In case of number of subjects within a stratum is too small for a meaningful analysis, the strata may be combined to obtain larger cell size. The least squares mean (LSM) and SE, 95% confidence interval (CI) and associated p-values for each treatment groups, as well as for each treatment group comparison of interests. To account for possibility of unequal variances between the groups, the ANCOVA model will be implemented within mixed model framework where <repeated/group=> option will be used to allow separate estimation of residual variances for different groups.

Each of the comparisons within the co-primary endpoint family will be conducted at a significance level of 0.05. If and only if all three testing achieve statistical significance, the study is claimed to meet its primary objective and the hypothesis testing will continue to secondary endpoints, otherwise all statistical comparisons for secondary endpoints are considered descriptive only.

An example Statistical Analysis System (SAS) code for ANCOVA analysis is shown as below:

```
PROC MIXED DATA=adx ;  
  class armcd stratum;  
  model pchg = blres armcd stratum / solution ddfm=kenwardroger;  
  repeated/ group=armcd;  
  lsmeans armcd / diff;
```

Missing values for primary endpoint will be imputed using multiple imputation method, taking account for the adherence to the treatment. For patients with missing data and no longer receiving treatment at Week 12 (defined as lab date is > 7 days post last dose of IMP), their LDL-C will be imputed as their baseline value, for those with missing data but still receiving treatment, their LDL-C value will be imputed using a regression model based imputation model including treatment, stratification factor, baseline LDL-C as auxiliary variables. The imputation will be performed for 200 times and imputed datasets will be analyzed using an ANCOVA model with treatment, stratification as factors and baseline LDL-C as a covariate. Approximately 200 imputed datasets will be created; results from the analysis of each imputed dataset will be combined using Rubin's method. The final combined least squares mean (LSM) and standard error (SE) will be provided for both treatment groups, along with the LSM for each treatment comparison, its 95% confidence interval (CI) and associated p-value. More details will be provided in the programming specifications.

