10.5.3. Treatment Week 4 (Visit T2; Day 29 ± 5 days)

Patients will undergo the following assessments and procedures:

- Concomitant medication review (ongoing);
- Assess AEs and SAEs;
- Weight;
- Vital signs;
- Central clinical laboratory evaluations:
 - Hematology, blood chemistry, and urinalysis;
 - Basic fasting lipids (TC, calculated LDL-C, HDL-C, non-HDL-C, and TG);
- Trough PK sample;
- Return of IMP; assessment and recording of IMP dosing adherence;
- IWRS contact to obtain new MED ID number for double-blind IMP;
- Dispense double-blind IMP and provide dosing and storage instruction.

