10.6.4. Patient Discontinuation from the Study

Patient discontinuation prior to the patient's completion of the study is expected to be uncommon, occurring only if the patient explicitly withdraws consent. At the time of discontinuing from the study, the Medical Monitor should be contacted, and, if possible, an early discontinuation visit should be conducted, per the Study Schedule. The patient will be permanently discontinued both from the IMP and from the study at that time. During the study closeout period, survival (vital) status will be collected within legal and ethical boundaries for all patients randomized who withdrew their participation from the study.

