11. ASSESSMENT OF EFFICACY

11.1. Assessments of Lipids and hs-CRP

Central clinical laboratory samples will be collected and analyzed for the parameters detailed in Table 3. LDL-C will be calculated or measured directly if TG are >400 mg/dL or LDL-C is <50 mg/dL.

Blood draws for lipids (not safety) must meet the criterion below. If this criterion has not been met, these blood samples will NOT be collected. **If this criterion can be met by rescheduling clinic visit to occur within 3 days, these blood samples will be collected at the rescheduled clinic visit only.**

- Blood samples will be drawn after a minimum 10-hour fast (water and concomitant medications are allowed)

Patients are to be in a seated position during the blood collection. Collection schedule and instructions are provided in the Central Clinical Laboratory Manual. A description of the sample collection, storage, and shipping as well as monitoring and management of abnormal laboratories are described in [Section 12.1.6](#).

When vital signs and laboratory samples are to be collected at the same time point, vital sign measurements will precede laboratory sample collection.

Table 3: Central Clinical Laboratory Parameters (Lipids and hs-CRP)

Clinical Laboratory Test	Clinical Laboratory Test
Basic Lipid Parameters 
• Total cholesterol (TC)• Calculated low-density lipoprotein cholesterol (LDL-C) and non-HDL-C• High-density lipoprotein cholesterol (HDL-C)• Triglycerides (TG)	Other Parameters 
• High-sensitivity C-reactive protein (hs-CRP)• Apolipoprotein B (ApoB)

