14.5. Co-Primary Endpoint Analysis

The co-primary efficacy endpoints consist of three comparisons of the percent change from baseline to Week 12 in LDL-C: FDC vs. placebo, FDC vs. EZE; and FDC vs. BA.

Each of the comparisons will be carried out using an analysis of covariance (ANCOVA) model including treatment group and stratification factors as factors and baseline LDL-C as covariate.

Baseline LDL-C is defined as the mean of the values from Week -2 (Visit S1) and pre-dose Day 1/Week 0 (Visit T1).

Missing values for primary endpoint will be imputed using multiple imputation (MI) method (MI), taking account for the adherence to the treatment. For patients with missing data and no longer receive treatment at Week 12, their LDL-C will be imputed as their baseline value; for those with missing data but still receiving treatment, their LDL-C value will be imputed using a regression based model including treatment, stratification factors, baseline LDL-C as auxiliary variables. Approximately 200 datasets will be imputed. The imputed datasets will be analyzed using the ANCOVA model described above and the results from the analysis of each imputed dataset will be combined using Rubin's method. The final results will include the least squares mean (LSM), SE, 95% confidence interval (CI) and associated p-values for each treatment group, as well as for each treatment group comparison of interests.

The details of the ANCOVA model and multiple imputations will be further described in the SAP.

[figure not shown]
Each of the comparisons within the co-primary endpoint family will be conducted at a significance level of 0.05. If and only if all three testing achieve statistical significance, the study is claimed to meet its primary objective and the hypothesis testing will continue to secondary endpoints, otherwise all statistical comparisons for secondary endpoints are considered descriptive only.

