⁸ Clinical safety labs include hematology, blood chemistry, and urinalysis. Coagulation panel only if receiving anticoagulants that in the investigator's judgement requires monitoring (then test at T1 and repeat 3-5 days after starting IMP).

⁹ Basic fasting lipids include total cholesterol, calculated LDL-C, HDL-C, non-HDL-C, and triglycerides.

¹⁰Includes apoB and hs-CRP.

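### Imputation for patients missing Week 12 LDL-C on treatment names only the ANCOVA terms, and no planned analysis uses Week 4 and Week 8 LDL-C to test it

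*SAP*

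**What the plan says.** SAP 5.3.1 splits patients with no Week 12 LDL-C into two groups. Those no longer on treatment are set to their baseline value; that rule is not at issue here. For those still on treatment, "their LDL-C value will be imputed using a regression model based imputation model including treatment, stratification factor, baseline LDL-C as auxiliary variables". Protocol 14.5 says the same: "their LDL-C value will be imputed using a regression based model including treatment, stratification factors, baseline LDL-C as auxiliary variables".

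The analysis model in SAP 5.3.1 is described in these words: "An ANCOVA with treatment group and randomization stratification as factors and baseline LDL-C as a covariate will be performed to compare treatment groups". The SAP then adds "More details will be provided in the programming specifications".

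LDL-C is drawn between baseline and Week 12. Protocol 10.5.3 (Week 4) lists "Basic fasting lipids (TC, calculated LDL-C, HDL-C, non-HDL-C, and TG"), and 10.5.4 (Week 8) lists the same panel. The schedule in Appendix 1 marks both visits, and its footnote 9 reads "Basic fasting lipids include total cholesterol, calculated LDL-C, HDL-C, non-HDL-C, and triglycerides".

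SAP 5.3.3 plans two sensitivity analyses: the treatment completer set and the observed FAS data, neither with imputation. SAP 5.2.1.3 requires a Week 12 LDL-C for membership of the completer set.

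**The concern.** The imputation model calls its three terms auxiliary, but none of them adds anything to the analysis model. A regression imputation built on the analysis covariates carries no new information about the missing patients. It assumes that, within arm, stratum and baseline level, a patient who misses Week 12 on treatment responds like one who attends. Week 4 and Week 8 LDL-C are the obvious data for relaxing that assumption, and they are already scheduled.

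The sensitivity analyses make essentially the same assumption for these patients, so agreement between them and the primary analysis would say little about this group.

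All three comparisons must succeed for the trial to meet its objective. If on-treatment missingness depends on response, and does so differently between arms, a comparison is shifted. A worse pattern in the FDC arm overstates its effect, a worse pattern in the comparator understates it, and equal patterns cancel.

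**Working it through.** **Plan's own figures.** The only relevant one is the sample size: 3 x 100 + 50 = 350. The available text gives no SD, effect size, power or missing rate, so the inputs below are assumptions.

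**Step 1: compare the models and look for a test.**

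| Place | What it uses |
|---|---|
| On-treatment imputation (SAP 5.3.1, Protocol 14.5) | treatment, stratification, baseline LDL-C |
| ANCOVA (SAP 5.3.1) | treatment, stratification, baseline LDL-C |
| Completer analysis (SAP 5.3.3, 5.2.1.3) | only patients with Week 12 LDL-C |
| FAS observed-data analysis (SAP 5.3.3) | only patients with Week 12 LDL-C |
| Subgroups (SAP 5.3.4) | no imputation |
| By-visit summaries (SAP 5.3.2) | interim values, descriptive only |
| SAP addenda | repeat the imputed table, or use completer or observed Week 12 data; one by-visit LDL-C summary |

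Pattern mixture model is in the SAP's abbreviation list, but no such analysis is described.

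**Step 2: does imputing on the ANCOVA terms differ from dropping the patients?** In 100 simulated trials with 5% missing and 200 imputations, the two estimates differed by 0.0004 point on average and by at most 0.17. A second simulation had 2-10% missing both on and off treatment, imputed in mg/dL and analyzed percent change. The mean gap was 0.01-0.08 point if off-treatment patients were set to baseline before the regression was fitted, and 0.02-0.25 if after. The SAP does not state the order. So the branch is approximately, not exactly, equal to dropping.

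**Step 3: size if missingness depends on Week 8 response.** Assume SD 20 points, Week 8 to Week 12 correlation (rho) 0.6-0.75, and odds of missing Week 12 multiplied by 2 or 3 per SD of worse Week 8 response (z8), in the FDC arm only. With logit P(missing) = a + ln(OR) x z8, and a solved for the stated rate,

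bias = rho x SD x E[z8 | observed].

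Absolute values:

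| Missing | OR | E[z8 given observed] | rho 0.6 | rho 0.75 |
|---|---|---|---|---|
| 2% | 2 | 0.0137 | 0.16 | 0.21 |
| 2% | 3 | 0.0212 | 0.25 | 0.32 |
| 5% | 2 | 0.0338 | 0.41 | 0.51 |
| 5% | 3 | 0.0510 | 0.61 | 0.77 |
| 10% | 2 | 0.0662 | 0.79 | 0.99 |
| 10% | 3 | 0.0978 | 1.17 | 1.47 |

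For example, 0.75 x 20 x 0.0978 = 1.47.

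Standard errors: 20 x sqrt(2/100) = 2.83 for FDC versus each component, and 20 x sqrt(1/100 + 1/50) = 3.46 versus placebo. The range is thus from 0.16/2.83 = 0.06 to 1.47/2.83 = 0.52 of a standard error.

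If the dependence holds in both arms, the bias is 0 at equal rates. At 10% in one arm and 5% in the other it is 0.39-0.70, with the sign set by which arm is worse.

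**Step 4: what adding interim LDL-C would do** (point ranges over OR 2-3 and rho 0.6-0.75).

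| Situation | 2% | 5% | 10% |
|---|---|---|---|
| Week 8 dependence, named model | 0.16-0.32 | 0.41-0.77 | 0.79-1.47 |
| Same, Week 8 added but absent in half of the missing | 0.08-0.15 | 0.20-0.37 | 0.40-0.70 |
| Dependence on the unobserved Week 12 value, named model | 0.27-0.42 | 0.67-1.02 | 1.32-1.96 |
| Same, Week 8 added | 0.13-0.27 | 0.30-0.66 | 0.57-1.27 |

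If Week 8 is always observed and drives missingness, the bias is removed. If the unobserved Week 12 value drives it, about 44-65% remains, close to 1 - rho^2 (0.44-0.64).

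A separate simulation with different assumptions (SD 22, correlation 0.5-0.7, missingness in FDC only, log-linear in Week 8 response) gave biases of about 0.2-0.3, 0.6-0.8 and 1.2-1.65 points. Adding Weeks 4 and 8 recovered the full-data difference to within about 0.02.

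**The case against.** The strongest reply is that the group is small and the mechanism weak. Of a patient who leaves the study, Protocol 10.6.4 says "The patient will be permanently discontinued both from the IMP and from the study at that time", which tends to move leavers to the baseline rule. Patients who stop drug stay in follow-up (10.6.3). Draws that do not meet the fasting rule can be moved by up to 3 days (11.1: "these blood samples will be collected at the rescheduled clinic visit only"). Any visit from Day 63 counts as Week 12 (SAP 5.1). What remains is mostly missed visits and failed samples. Lipids are masked after randomization (Protocol 8.3), so response can affect attendance only indirectly, for example through adherence. All of this stands. It makes the 10% row look high and is why the point ranks low.

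Second, the SAP says its model is one including these terms and defers detail to programming specifications. That is fair: the text shows that interim LDL-C is not prespecified, not that the imputation omitted it.

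Third, the named model is a legitimate missing-at-random model, and adding Week 8 keeps the same kind of assumption. True, but it conditions on more of what is known.

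Fourth, by-visit LDL-C summaries are planned in both the FAS and the completer set, and comparing them gives a rough check. It does not isolate this group, because completers also exclude patients who stopped treatment.

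Last, at 2% missing the bias (0.16-0.32) is comparable with the effect of the unstated imputation order (up to 0.25). That also stands.

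**Conclusion.** The concern holds as a low-priority robustness gap. As written, the plan treats patients missing Week 12 LDL-C on treatment approximately as if they had been dropped. It names no interim LDL-C for imputing them, and no planned analysis tests that choice.

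The likely size is a few tenths of a point at 2-5% missing and up to about 1.5 points at 10% under Week 8 dependence, always below one standard error of the comparison. These figures rest on an assumed SD, correlation, odds ratio and missing rate, and on dependence confined to one arm. The direction is unknown. It is not an error in the primary analysis, and no changed conclusion is shown. It falls away if the programming specifications already name interim LDL-C, or if the number of such patients is near zero.

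**What to change.** 1. Report, by arm, how many patients miss Week 12 LDL-C while on treatment. State the classification rule: SAP 5.3.1 defines off treatment by the lab date relative to the last dose, and a patient with no Week 12 draw may have no lab date. A count near zero closes the point.
2. Otherwise, repeat the imputation with Week 4 and Week 8 LDL-C as added predictors in the on-treatment model, and state how intermittent gaps are handled. Leave the ANCOVA and the off-treatment baseline rule unchanged.
3. The first SAP addendum says that the planned analyses were completed and the study unblinded. Present the result as one table labelled post hoc beside the unchanged primary, and note that it removes bias only where missingness depends on observed interim LDL-C.
4. The same model can serve non-HDL-C and TC with their own interim values, since SAP 5.3.2 imputes them as for the primary endpoint. It does not carry over directly to apoB, which is not drawn at Weeks 4 and 8. No size is claimed for these endpoints.

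The cost is some imputation code and one table, with no new data. If the count is near zero, the count alone is enough.

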5.3.2 Secondary and Exploratory Efficacy Endpoint Analyses

Key secondary efficacy endpoints, which include the percent change from baseline to Week 12 in LDL-C, non-HDL-C, TC, and apoB, will be analyzed in a similar manner as the primary efficacy endpoint.

For hsCRP, a non-parametric (Wilcoxon rank-sum test) analysis with Hodges-Lehmann estimates and confidence interval will be performed because based on historical knowledge, publication precedence (Brendan etc., 2006) and recent data available, hsCRP is known to be skewed by extreme values and have non-normal distribution. HDL and TGs will be summarized using descriptive statistics for the observed value and the change/percent change from baseline at each protocol scheduled visits.

If co-primary endpoint family achieves statistical significance, a list of selected secondary endpoints will be tested in sequential order within each comparison group. The alpha allocation among the three comparison groups is: alpha = 0.01 for FDC vs. Placebo alpha = 0.02 for FDC vs. EZE; alpha = 0.02 for FDC vs. BA.

Missing values for these secondary endpoints will be imputed using multiple imputations method as described for primary endpoint. All other secondary endpoints not included in the step-down procedure (Figure 2) will be tested at significant level of 0.05 without multiplicity adjustment. Only observed data will be used for these analysis.

Other secondary endpoints of HDL-C and TGs will be summarized using descriptive statistics at week 12.

[figure not shown]
By-visit summary for all efficacy endpoints (LDL-C, non-HDL-C, TC, ApoB, hsCRP, HDL-C and TGs) using FAS and treatment completer set will be provided for both conventional and standard units.

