- Percent change in LDL-C from baseline at Week 12 in BA 180 mg + EZE 10 mg FDC arm compared to BA 180 mg arm;
- Percent change in LDL-C from baseline at Week 12 in BA 180 mg + EZE 10 mg FDC-treated arm compared to EZE 10 mg arm.

The study is considered to have successfully demonstrated its primary objective IF all 3 co-primary endpoints achieve statistical significance.

Secondary endpoints:

- Percent change from baseline at Week 12 in parameters below between the BA 180 mg + EZE 10 mg FDC-treated arm and placebo arm, BA 180 mg-treated arm or EZE 10 mg arm:
 - hs-CRP;
 - Non-HDL-C;
 - TC;
 - ApoB;
 - TG;
 - HDL-C.

Exploratory endpoints:

- Proportion of patients attaining LDL <70 mg/dL at Week 12 in BA 180 mg + EZE 10 mg FDC-treated arm compared to BA 180 mg arm, EZE 10 mg arm and placebo arm;
- Plasma trough concentrations at Weeks 4, 8, and 12 of BA (ETC-1002 and its active metabolite ESP15228) and EZE (glucuronidated EZE and unconjugated EZE) in BA 180 mg + EZE 10 mg FDC-treated arm, BA-treated arm, and/or EZE alone treated arm.

Safety endpoints:

- Patient incidence of TEAE;
- Safety laboratory values, vital signs, PE findings, and ECGs.

Statistical Methods:

Sample Size

[figure not shown]
The sample size of 100 patients per active treatment group and 50 placebo patients (2:2:2:1) in this study (350 patients total) is selected to provide adequate power for each of the co-primary endpoint as well as the co-primary endpoint family as a whole.

Testing Procedures

The co-primary endpoint family will be tested first, and each co-primary endpoint will be tested at alpha level of 0.05. The testing will stop if any of the co-primary endpoints does not achieve statistical significance. The secondary endpoints will only be tested when ALL of the co-primary endpoints are significant. A hierarchical testing procedure will be implemented within each comparison group on selected secondary endpoints.

Each of the secondary endpoint within a comparison group will be tested only if previous endpoint is significant at the alpha level assigned for that comparison group, i.e., via a step-down procedure.

A schematic representation for the statistical testing of the treatment comparisons and the co-primary and secondary efficacy endpoints is provided below.

Analysis Populations

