For the selected secondary endpoints (percent change from baseline to Week 12 in non-HDL-C, apoB, TC, and hsCRP), the data will be analyzed in the similar fashion as for the primary endpoints and then the step-down procedure as detailed above will be applied to the analysis results for each treatment comparison of interest (BA 180 mg + EZE 10 mg FDC versus placebo; BA 180 mg + EZE 10 mg FDC versus BA 180 mg; BA 180 mg + EZE 10 mg FDC versus EZE 10 mg). Other secondary endpoints based on HDL-C and TG will be analyzed separately outside of the step-down procedure. For HDL-C, non-HDL-C, TG, and TC, baseline is defined as the mean of the values from Week -2 (Visit S1) and predose Day 1/Week 0 (Visit T1), while baseline for apoB and hs-CRP is the predose Day 1/Week 0 value.

Safety Analyses

The summarization of AEs will include only TEAEs, any unfavorable and unintended sign, symptom, or disease occurred or worsened in severity since the first dose of the IMP until 30 days after study completion whether or not related to the product. An SAE is defined as any untoward medical occurrence that occurs at any dose that results in death, is life-threatening, requires inpatient hospitalization, results in persistent or significant disability, or results in a congenital anomaly/birth defect. TEAEs and SAEs will be summarized by system organ class (SOC), severity, and relationship to study drug for each treatment group.

Clinical safety laboratories, including hematology, blood chemistry, HbA_{1C}, glucose, and urinalysis; PE findings; vital signs; ECG readings; and weight will be summarized by the value and by change from baseline in the value (where appropriate) at each post baseline time point.

TABLE OF CONTENTS

1.	TITLE PAGE.....	1
2.	SYNOPSIS	2
3.	LIST OF ABBREVIATIONS AND DEFINITIONS OF TERMS.....	18
4.	INTRODUCTION	22
4.1.	Cardiovascular Disease and LDL-C-Lowering Drugs	22
4.2.	Background on Bempedoic Acid.....	24
4.2.1.	Mechanism of Action	24
4.2.2.	Nonclinical Experience.....	24
4.2.3.	Previous Human Experience.....	25
4.2.4.	Dose Selection	26
4.3.	Background on Ezetimibe.....	26
4.4.	Risk Benefit Summary.....	26
5.	TRIAL OBJECTIVES AND PURPOSE.....	27
5.1.	Objectives	27
5.1.1.	Primary Objectives	27
5.1.2.	Secondary Objectives	27
5.1.3.	Exploratory Objective:.....	27
5.2.	Study Endpoints.....	27
5.2.1.	Primary Endpoint.....	27
5.2.2.	Secondary Endpoints	27
5.2.3.	Exploratory Endpoints.....	28
5.2.4.	Safety Endpoints.....	28
6.	INVESTIGATIONAL PLAN.....	29

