14.6. Secondary Efficacy Endpoint Analyses

Secondary efficacy endpoints, which include the percent change from baseline to Week 12 in additional lipid and cardiometabolic biomarkers, will be analyzed in a similar manner as the primary efficacy endpoint.

Baseline for non-HDL-C, HDL-C, TC, and TG is defined as the mean of the values from Week -2 (Visit S1) and predose Day 1/Week 0 (Visit T1), while baseline for ApoB and hs-CRP is defined as the predose Day 1/Week 0 (Visit T1) value.

As described in Section 14.5, if co-primary endpoint family achieves statistical significance, a list of selected secondary endpoints will be tested in sequential order within each comparison group. The alpha allocation among the three comparison groups is: alpha = 0.02 for FDC vs. EZE or FDC vs. BA; alpha = 0.01 for FDC vs. Pbo

All other secondary endpoints not included in the step-down procedure will be tested at significant level of 0.05 without multiplicity adjustment.

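### The secondary sequences are tested at fixed levels of 0.01, 0.02 and 0.02, and no visible text passes a completed sequence's alpha on: a valid plan, but a missed efficiency unless Figure 2 already shows transfer

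*SAP*

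**What the plan says.** The co-primary gate comes first. SAP 5.3.1 states: "Each of the comparisons within the co-primary endpoint family will be conducted at a significance level of 0.05". All three tests must succeed before any secondary endpoint is tested formally.

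SAP 5.3.2 then sets the secondary levels: "The alpha allocation among the three comparison groups is: alpha = 0.01 for FDC vs. Placebo", followed by "alpha = 0.02 for FDC vs. EZE; alpha = 0.02 for FDC vs. BA". Protocol 14.6 has the same split ("alpha = 0.02 for FDC vs. EZE or FDC vs. BA; alpha = 0.01 for FDC vs. Pbo"), and the SAP makes clear that 0.02 applies to each active comparison.

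Within a comparison, Protocol 14.6 says that "a list of selected secondary endpoints will be tested in sequential order within each comparison group". The Synopsis (Testing Procedures) adds that each secondary endpoint is "tested only if previous endpoint is significant at the alpha level assigned for that comparison group". It names four endpoints for the step-down: non-HDL-C, apoB, TC and hs-CRP.

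No sentence in either document moves alpha from one comparison to another. Both documents also refer to a diagram of the testing procedure (a schematic in the Protocol Synopsis, Figure 2 in the SAP). Neither image is available in the text reviewed. That is not a gap in the plan, but it limits what can be concluded.

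**The concern.** The text names one assigned level per comparison. Read literally, when every endpoint in one sequence is significant, that comparison's alpha has no further use. A Bonferroni-based graphical procedure would hand it to the sequences still open. It keeps familywise error within the same 0.05 limit and cannot lose a rejection that the fixed split would make.

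At stake are the endpoints late in a sequence. A secondary claim with a p-value between 0.02 and 0.05 in one active comparison would fail even if the other two sequences had been completed.

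**Working it through.** **Inputs from the documents.** Secondary levels 0.01, 0.02, 0.02 (SAP 5.3.2); arms of 100, 100, 100 and 50 (SAP 4.3).

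**Assumptions.** The documents give no effect size, SD or target power for any endpoint, so all power figures below are assumed. Tests are taken as two-sided, SDs as equal across arms, and a normal approximation stands in for the Wilcoxon test of hs-CRP. Each sequence is represented by its last endpoint, with the earlier ones taken as passed.

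**1. The plan's own split.** 0.01 + 0.02 + 0.02 = 0.05. The written procedure is valid at 0.05.

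**2. What transfer in proportion to initial alpha would do.**
- Placebo sequence completed: EZE and BA each get 0.01 × 0.02/0.04 = 0.005, so each moves to 0.025.
- EZE sequence completed: placebo gets 0.02 × 0.01/0.03 = 0.0067 (to 0.0167) and BA gets 0.0133 (to 0.0333).
- Two sequences completed: the third is tested at 0.05.

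**3. Power of an active comparison's last endpoint at fixed levels.** For 80% power at 0.05 the expected z is 1.960 + 0.842 = 2.802, which at 100 vs 100 is 2.802 × √(2/100) = 0.396 SD. Power is Φ(2.802 − critical value):

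| Level | Critical value | Power |
|---|---|---|
| 0.02 | 2.326 | 68.3% |
| 0.025 | 2.241 | 71.2% |
| 0.05 | 1.960 | 80.0% |

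**4. Power with recycling.** I simulated 400,000 trials per scenario. The shared FDC arm gives correlations of 0.01/0.02 = 0.5 (EZE with BA) and 0.01/√(0.03 × 0.02) = 0.41 (either with placebo).
- Placebo strong, the other active sequence also at 80%: 68% to 76%.
- Both other sequences strong (expected z = 4): 68% to 79%.
- Rejections made by the fixed split and lost with recycling: none.

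**5. Range over effect size**, active comparison, both other sequences completed (0.02 against 0.05):

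| Effect (SD) | Fixed 0.02 | At 0.05 | Gain (points) |
|---|---|---|---|
| 0.3 | 42% | 56% | 14 |
| 0.4 | 69% | 81% | 12 |
| 0.5 | 89% | 94% | 5 |
| 0.8 | about 100% | about 100% | about 0 |

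**6. FDC vs placebo.** If the components contribute equally and additively, 0.396 SD against each component implies 2 × 0.396 = 0.792 SD against placebo. The expected z is 0.792/√(1/50 + 1/100) = 4.57. Power is 97.7% at 0.01 and 99.5% at 0.05, so the gain is at most about 2 points.

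**7. Error.** Under the global null, simulated familywise error is about 0.045 with either procedure. When two comparisons are truly effective and only the third's last endpoint is null, the error on that endpoint is 0.02 (BA) or 0.01 (placebo) under the fixed split. With transfer it is 0.05 in both cases, which is still at the limit.

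**The case against.** The strongest objection is that the defining figure cannot be seen. A schematic is a usual place for transfer arrows, and 0.01, 0.02 and 0.02 are also what starting weights would look like. The Synopsis wording leans towards fixed levels but does not exclude transfer. This stands: any loss of power is conditional on Figure 2 showing none.

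Second, a Bonferroni split with fixed sequences inside it is a legitimate conservative choice. This also stands. A reader might infer that the secondary testing is flawed; it is not.

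Third, a reader might infer that the fixed split gains nothing in error control. That is true only against the 0.05 ceiling. Step 7 shows that the actual error on a null last endpoint can be as low as 0.01 to 0.02 under the current text.

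Fourth, a reader might infer that FDC vs placebo loses most, since it has the smallest arm and the strictest level. An endpoint with 80% power at 0.05 does have only 59% at 0.01. But 80% power there corresponds to 2.802 × √0.03 = 0.485 SD, while active comparisons at z = 4 correspond to 4 × √0.02 = 0.566 SD. FDC would then beat each component by more than it beats placebo, making each component about 0.08 SD worse than placebo. Protocol 6.2 hypothesises the opposite, that both components contribute. The documents do not support a large placebo gain.

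Finally, both SAP addenda, dated December 2018, say that the planned analyses were complete and the data unblinded. A change to the secondary levels after that would be a post-hoc change in multiplicity control. This limits when the fix can apply; it does not alter the point about the plan as written.

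**Conclusion.** The point holds as a missed efficiency in the secondary tests, conditional on Figure 2 showing no transfer. Where the last endpoint of FDC vs EZE or FDC vs BA has moderate power (80% at 0.05), recycling is worth about 8 to 11 points: 68% to 76% or 79%. With large effects it is worth almost nothing, and for FDC vs placebo about 1 to 2 points under equal additive contributions. Familywise error remains at or below 0.05 either way.

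The sizes rest on assumed effects and on the shared-arm correlations. The direction does not, because transfer can only add rejections. The documents do not show which sequence would actually fall short.

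**What to change.** Check Figure 2 and the Protocol schematic first.

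- If they show no transfer, add to SAP 5.3.2, for the plan as set before unblinding: when all endpoints in a comparison's sequence are significant, its alpha passes to the remaining comparisons in proportion to their initial alpha, and testing resumes there at the increased level (Bonferroni-based graphical procedure). Keep the starting levels of 0.01, 0.02 and 0.02 and the order within each sequence.
- If they do show transfer, state the same rule and weights in the text of SAP 5.3.2 and Protocol 14.6.

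The cost is one sentence, with no extra patients or data and no rejection given up. The price in error is that a null last endpoint may be tested at up to 0.05 instead of 0.01 or 0.02. The rule must not be used retrospectively to claim further significant secondary results from the unblinded data.
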